Approval from the Danish Data Protection Agency, the Danish Medicines Agency and local ethics committee will be achieved before initiation of the trial. The Trial will be registered at Clinicaltrial.gov, as has been recommended by the ICMJE (International Committee of Medical Journal Editors).

Collected data will continuously be registered and filled into each patient's CRF, which will be ready before the initiation of the trial. Data will be stored confidentially for 10 years, and afterwards destroyed.

Investigators will be allowed direct access to source data and documents, among these patients' journals.

The information needed from the patients' journals include information regarding current and prior diseases, medical treatment and all information related to their cancer treatment including blood works, histology and imaging. At auditing, monitoring and/or inspection from the Danish Medicines Agency, GCP-unit or from other relevant authorities these will be allowed relevant access to information.

If a patient withdraws from the study the collected data will be used in an anonymous manner, unless the patient requests that the data should be erased. After completion of the CRF the data will be transferred into a predesigned trial database. Double data entry will be performed in order to insure the best possible transfer of data. At the end of the trial the principle investigator will archive all the CRFs in the final database.

QUALITY CONTROL AND QUALITY ASSURANCE

Existing procedures for quality assurance and quality control will be followed. An agreement with the GCP unit will be made to handle monitoring at the beginning, mid-term and at the end of the project.

DATA AND STATISTICAL ANALYSIS

Statistical analysis will be performed using the SAS® Proprietary Software 9.4, SAS Institute Inc., Cary, NC USA. Data will be analyzed via parametric or non-parametric statistic depending on their distribution. Log-transformation will be applied when possible. A two-sided P-value of less than 0,05 will be considered statistical significant. For baseline characteristics, descriptive statistics will be used. In case of multiple comparisons the appropriate statistical correction will be applied. No interim analysis is planned for the study. Intention to treat analyses will be performed.

PUBLICATION

When the last patient has finished the trial the regional ethical committee will be notified within 90 days and a final rapport will be sent within 12 months. The data will be made available on EudraCT in accordance

with the current legislation. Submission of manuscripts for publication will be aimed at an international established journal with high impact and the intended timeframe of publication is within 1 year. The primary outcomes will be reported in a main publication, and the results will be made available at clinicaltrials.gov and on www.clinicaltrialsregister.eu. Both positive, negative and inconclusive trial results will be published.

INSURANCE

There is in relation to this project not taken further assurance measures than those applicable to patients who are part of routine clinical care in hospitals and in clinical trials.

ECONOMY

Initiator of this study is [name]. No private party has any part in the study.

Financial support from grants to cover the expenses will be applied on an ongoing basis.

The responsible investigators are employees of Slagelse hospital and University Hospital Zealand. The investigators have no economic conflicts of interest in this study.

No considerations will be paid to the participating patients.

BUDGET

Salary Ph.D-student [name] 2½ years	1.200.000kr	Money has been granted
Metformin for 24 patients	9000kr	
Placebo for 24 patients	9000kr	
Randomization and handling of study medication	25.000kr	
Cancer cell line examinations	100.000kr	
Immunohistochemistry of tumor samples	90.000kr	

PAX-gene tubes	41.000kr	
Analyses of blood samples	300.000kr	
GCP-monitoring	25.000kr	
Notification to the Danish Medicines Agency (Lægemiddelstyrelsen)	7.734kr	
Total	1.806.734kr	

REFERENCES

1. Dccg. Landsdækkende database for kræft i tyk - og endetarm (DCCG) National årsrapport 2014. *Dccg*. 2014;(december):1-182.
2. Hugen N, Wilt JHW De, Nagtegaal ID. Metastatic pattern in colorectal cancer is strongly influenced by histological subtype. 2014;534-540. doi:10.1093/annonc/mdt591.
4. Lee JH, Kim T Il, Jeon SM, Hong SP, Cheon JH, Kim WH. The effects of metformin on the survival of colorectal cancer patients with diabetes mellitus. 2012;759(January 2000):752-759. doi:10.1002/ijc.26421.

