To our knowledge no trials examining the effect of metformin on changes in expression of Ki67 and cleaved caspase 3 in colon cancer exist. Studies on endometrial cancer patients treated with metformin have shown varying results. One study found a decrease in Ki67 expression of 11,75% in 20 patients³⁶, another a decrease of 44 % in 31 patients³⁷ and a third found a decrease of 17,2% in 28 patients³⁸. We have chosen a sample size of 24 patients in each group based on these findings. The patients will be randomized in blocks of six and therefore the study will proceed until 24 patients have been enrolled in each arm. The study of the effect of metformin on postoperative hyperglycemia and insulin resistance is exploratory.

TRIAL STRUCTURE AND RESPONSIBILITIES

The principle investigator (EC) is responsible for the preparation of the protocol, CRF, coordinating meetings of the steering committee, and implementing decisions into daily operations of the trial. Furthermore, the principle investigator will along with a team of co-investigators take care of screening, recruitment, data collection, and completion of individual CRF's at the trial location. The steering committee consists of four members (EC, TF, LCT and IG) and its purpose is to overview the progress and safety of the trial. Meetings will be held every 3 months as standard and in case of Severe Adverse Events (SAE) or other serious incidents an extra meeting will be held accordingly. The study will be monitored by the local GCP unit.

EFFECT PARAMETERS

The primary outcome is determination of the difference of the level of proliferation after the intervention (time of surgery) adjusted for the level seen at baseline (time of colonoscopy).

A secondary outcome is the difference in the level of apoptosis after the intervention adjusted for levels seen at baseline. Subgroup analysis in regards to the most common mutations will be performed.

The level of proliferation will be defined as the percentage of tumor nuclei showing Ki67 staining in a specific microscopic field, whereas the level of apoptosis is defined as the absolute number of tumor cells expressing cytoplasmic and perinuclear staining of cleaved caspase-3 at the transition zone³⁹.

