Also the effect of metformin will be measured by examining the difference in proliferation, migration and adhesion of colon cancer cell lines treated with plasma from the patients. Blood samples stored in a biobank will be analyzed for metabolic and immunological changes.

The effect of metformin on enterocytes and hepatocytes will be analyzed on biopsies taken at time of surgery. The effect of metformin on relevant pathways in the tissue specimens will be evaluated using mRNA sequencing, immunohistochemistry and peptide extraction.

The effect of metformin on the composition of the gut microbiome will be analyzed on fecal samples collected before initiation of study medication and before surgery. The composition of the microbiome in blood will be analyzed before and after surgery.

Finally the effect of metformin on postoperative hyperglycemia and insulin resistance will be measured by analyzing the difference in insulin resistance and plasma glucose levels before surgery and on postoperative day 1, 2 and 10.

We hypothesize that treatment with metformin, reduces the post-operative hyperglycemia and insulin resistance and in this way, enhances recovery. Patient perceived quality of recovery should be in focus when implementing new treatments and therefore, we include the widely used and validated "Quality of Recovery" questionnaire in the short 15-item form as an outcome in our study. A 40-item quality of recovery score (the QoR-40 score) was developed by Myles and colleagues in 2000 and has since been widely used and extensively validated^{40,41}. The short 15-item score (the QoR-15 score) was derived from the QoR-40 score and has been fully validated and translated to Danish and has shown to perform as well as the QoR-40 score^{42,43}. The QoR-15 questionnaire results in a score of 0–150 with a high score indicating a good quality of recovery.

Postoperative complications within 30 days from surgery will be assessed and classified according to the Clavien-Dindo classification⁴⁴.

STUDY PARTICIPANTS

A total of 48 patients, 24 in each arm, is needed.

Inclusion criteria:

- Patients with adenocarcinoma of the colon planned for elective curative intended surgery at Slagelse hospital
- Age of 18 or above

- Must be able to understand and sign informed content
- Sufficient amount of representative tumor material from the biopsies taken at the initial colonoscopy must be present

Exclusion criteria:

- Patients diagnosed with diabetes mellitus

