- Patients who are receiving or have received metformin or other oral antidiabetics
- Impaired kidney function (eGFR < 60mL/min)
- Severe liver disease (defined as transaminases above X 3 normal levels)
- Participation in another pharmacological intervention trial
- Predictable poor compliance (for instance not speaking fluent Danish, mentally impaired)
- Presenting with metastatic disease
- Patients undergoing neoadjuvant chemotherapy
- Pregnancy or lactation (fertile women must have a negative serum or urine pregnancy test to participate)
- Fertile women who do not use safe contraception during the study period.

Following contraceptive methods are acceptable when used consistently and in accordance with both the product label and the instructions of the physician are:

- Oral contraceptive, either combined or progestogen alone
- Injectable progestogen
- Implants of levonorgestrel
- Estrogenic vaginal ring
- Percutaneous contraceptive patches
- Intrauterine device or intrauterine system with a documented failure rate < 1% per year
- Male partner sterilization (vasectomy with documented azoospermia) prior to female patient's entry into the study, and this male is the sole partner for that patient
- Double barrier method: condom with spermicidal agent (foam/gel/film/cream/suppository), condom and occlusive cap (diaphragm or cervical/vault cap) with vaginal spermicidal agent (foam/gel/film/cream/suppository)
- Allergy to metformin or placebo

Colon cancer is in virtually all elective cases diagnosed through colonoscopy. When colon cancer is suspected, biopsies are taken to confirm pathology indicating adenocarcinoma. After the colonoscopy and when adenocarcinoma is confirmed the patient visits the outpatient clinic for preoperative examination and treatment planning. The study participants for the study will at this time be included in the study. Blood samples will be taken before the patients receive metformin or placebo, before surgery and on postoperative day 1, 2 and 10. Height, weight and BMI are measured at time of preoperative examination and at time of surgery. 30 days postoperatively the patients will receive a phone call asking them about possible complications and the patients' journals will be assessed for complications as well.

Patients will be asked to answer a baseline questionnaire about their well-being after randomization and the QoR-15 questionnaire on postoperative day 1, 2, 10 and 30.

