The biopsies taken at the colonoscopy and biopsies from the specimen removed at surgery will be analyzed for Ki67 and cleaved caspase-3 expression through immunohistochemistry (please see below in the "methods" section).

The study participants are randomized to metformin or placebo at the time of preoperative examination. Eligible patients will receive metformin or placebo 500 mg once a day for two days, followed by 500 mg twice a day for two days and then 500 mg three times a day until 10 days after the operation (visit at the out-patient clinic). The treatment is discontinued at the day of surgery and recommenced afterwards with the first meal. The patients will after surgery receive 500mg three times a day again. In summary patients will receive metformin or placebo for 20 days before the operation and again 10 days after the operation.

[figure not shown]

Figure 1: Study course

If a participant withdraws the consent then the participant will leave the study. In case of severe medical emergency (e.g. stroke or severe sepsis) which results in emergency surgery, stay in an intensive care unit, or hospitalization before the planned operation, the patient is excluded from the study. No further data will be collected from these patients after leaving; however, previous collected data will be part of the final data analysis in an intention to treat analysis. If a patient needs a CT scan with intravenous contrast in the treatment period the medication will be stopped.

Each year around 170 patients with colon cancer are undergoing surgery at Slagelse Hospital. In total 48 patients are needed for the study and we expect an inclusion rate of 50%. Approximately 15% are diagnosed with diabetes and are not eligible for the study. The inclusion of patients is therefore expected to last for 8 months. Subsequently, there will be a 4 month time period for data analysis and manuscript preparations. The study will be initiated in the fall of 2017.

RANDOMIZATION, ALLOCATION, CONCEALMENT AND BLINDING

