The patients will initially be diagnosed by colonoscopy, where biopsies will be taken for analysis of tumor cell proliferation and apoptosis. The same analysis will be repeated at the time of surgery on samples from the removed tumor as well as analysis for the most common mutations. The expression of cell proliferation and apoptosis will be compared to results from the preoperative biopsy analysis to examine the effect of a maximum of 20 days of preoperative metformin treatment in patients without diabetes. Six biopsies will be taken at time of colonoscopy and from the removed specimen. The biopsies are taken randomly from the tumor surface and are afterwards fixated according to standard guidelines. Samples from the non-tumor-bearing part of the intestine are taken from the oral and anal end of the removed specimen.

Perioperatively, two small biopsies are taken from the surface of the liver (2x2x2mm). Tissue specimens will be distributed into relevant tissue media before storage in the research biobank. The effect of metformin on the enterocytes will be compared to the effects of metformin on hepatocytes.

The immunoscore is measured by immunohistochemistry. From the tumor at time of operation biopsies from the core and from the invasive margin will be taken. These biopsies are stained for CD3 and CD8 positive lymphocytes and the density of these are measured. The density of CD3 and CD8 will also be measured from the biopsies taken at colonoscopy. Part of this analysis will be performed by a laboratory in France under supervision of [name] who has developed the immunoscore.

The proliferation activity of a tumor can be estimated by immunohistochemical determination of specific cell cycle related proteins. To explore whether treatment with metformin changes the expression of markers for cell proliferation and apoptosis in CRC patients, immunohistochemical staining for Ki67 (proliferation) and cleaved caspase-3 (apoptosis) will be performed. Ki67, a widely used marker for proliferation⁴⁵, is present in the nuclei during all active phases of the cell cycle, but is absent during the resting G0 phase. The level of apoptosis can be evaluated by staining of the activated, cleaved form of the pro-apoptotic enzyme caspase-3 in the tumor cell cytoplasm. Caspase-3 is the final enzyme to become activated in the caspase cascade and the level of activated or cleaved caspase-3 is a reliable measure of the level of apoptosis.⁴⁵⁻⁴⁷

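### Randomised patients with a severe emergency before surgery leave the study and data collection, yet the analysis is called intention to treat

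*Combined protocol and SAP*

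**What the plan says.** The study-course text under Study Participants places randomisation at the preoperative examination, with about 20 days of study drug before surgery. It then sets a rule for patients whose severe medical emergency leads to emergency surgery, to a "stay in an intensive care unit, or hospitalization before the planned operation, the patient is excluded from the study". The next sentence reads "No further data will be collected from these patients after leaving; however, previous collected data will be part of the final data analysis", and it names the analysis: "previous collected data will be part of the final data analysis in an intention to treat analysis". The Intervention section and the Data and Statistical Analysis section also commit to intention to treat.

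Under Effect Parameters, the primary outcome is the "difference of the level of proliferation after the intervention (time of surgery) adjusted for the level seen at baseline". Apoptosis is defined at the same two time points. Post-operative glucose and insulin resistance, QoR-15 and 30-day complications are all timed from surgery.

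Under Sample size, "the study will proceed until 24 patients have been enrolled in each arm". The target counts enrolled rather than evaluable patients, and no replacement rule or allowance for loss is given. The statistical section states no method for missing outcomes.

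Some observation does continue after a patient leaves: 24 hours of side-effect monitoring (Intervention), and follow-up of sudden unexpected serious reactions until they end (Data and Adverse Events). The exclusion rule refers to neither.

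**The concern.** An intention-to-treat analysis needs outcomes from the patients who were randomised. Here the protocol instructs investigators not to collect the outcome in a group defined by what happened after randomisation. The earlier data that are kept include baseline Ki67, but a baseline value alone adds essentially nothing to a baseline-adjusted comparison at surgery.

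Two things are at stake. If emergencies occur at different rates in the two arms, the groups compared at surgery are not quite the groups that were randomised. In addition, patients who have just had a severe emergency, and are then operated on, drop out of the 30-day complication comparison.

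The point is narrow. It does not concern withdrawn consent, where stopping collection is proper. It does not concern patients who stop or under-take study drug, because they stay in and only the per-protocol set removes those below 75% compliance.

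**Working it through.** **Is the outcome really lost?** The order of events for an excluded patient is: colonoscopy biopsy (baseline Ki67 available), randomisation, emergency, exclusion with collection ended, and then possibly resection. Ki67 and caspase-3 at surgery and every post-operative measure fall after collection ends. Some of these patients could supply tissue, because emergency surgery is itself one of the triggers and a hospitalised patient may have the tumor resected later. A patient who is never operated on has no surgical or post-operative outcome under any rule.

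**Inputs.** From the documents: 24 patients per arm, 48 in total, two-sided 5% significance level. The plan states no power, SD, target difference or emergency rate, so 24 per arm cannot be reproduced. Assumed for illustration: 80% power at 24 per arm; emergency rates r of 1%, 2% and 5%; omitted patients differing from the rest of their arm by k = 0.5, 1 or 2 SD.

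**How many patients?** Expected number = 48r. Chance of at least one = 1 − (1 − r)^48.

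| Assumed rate | Expected exclusions | Chance of at least one |
|---|---|---|
| 1% | 0.48 | 38% |
| 2% | 0.96 | 62% |
| 5% | 2.40 | 91% |

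At 5%, the binomial chance of more than three exclusions is 22%, so the range of 1 to 3 used below is illustrative and not an upper limit.

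**Loss of power.** For a two-sample t-test with 24 v 24, the standardised difference detectable with 80% power is d = 0.826. At that d:

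- 23 v 24 (one lost): 79.1%
- 23 v 23 (two lost): 78.2%
- 22 v 23 (three lost): 77.3%

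**Possible bias.** Suppose all m omitted patients are in one arm and would have differed from the rest of it by k SD. The mean of the full arm then differs from the mean of the observed patients by m × k / 24.

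| Omitted (m) | k = 0.5 | k = 1 | k = 2 | k = 1 as share of d |
|---|---|---|---|---|
| 1 | 0.021 SD | 0.042 SD | 0.083 SD | 0.042/0.826 = 5% |
| 2 | 0.042 SD | 0.083 SD | 0.167 SD | 0.083/0.826 = 10% |
| 3 | 0.063 SD | 0.125 SD | 0.250 SD | 0.125/0.826 = 15% |

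The one-arm assumption is deliberately unfavourable. If exclusion is unrelated to arm, the chance that all fall in the same arm is 23/47 = 49% for two patients and (23/47) × (22/46) = 23% for three.

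**The case against.** The strongest reply is that this is a small matter and partly a defensible choice. The trial enrols patients for planned elective surgery to study up to 20 days of pre-operative treatment. Tissue removed in an emergency, perhaps during sepsis and after shortened exposure, may not measure that effect. The triggers named as examples are stroke and severe sepsis, while the protocol describes metformin's side effects as primarily mild and gastrointestinal, and the lactic acidosis risk as very low. Patients, investigators and the pathologist are blinded. All adverse events are registered, so the triggering emergency would be on record. A simpler remedy would be to call the analysis complete-case or modified intention to treat.

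Much of this stands as a limit on size. No passage shows that emergencies would differ by arm, and some outcomes cannot be recovered. The post-operative glucose and insulin-resistance work is also declared exploratory.

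The reply does not remove the fault. Blinding limits unequal decisions to exclude, but not unequal event rates. Short exposure is something intention to treat accepts, and the per-protocol analysis and a sensitivity analysis can address it. Relabelling would make the description accurate, but it would leave obtainable data uncollected, and those data cannot be recovered afterwards.

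**Conclusion.** The concern holds. The exclusion rule conflicts with the intention-to-treat commitment made in the same sentence and repeated in two other sections. This is a stated instruction, not a gap in the text.

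The consequence is probably small: under the assumptions used, a few patients at most rates considered, one to three percentage points of power when one to three patients are lost, and a shift of 5% to 15% of the detectable effect at a 1 SD difference. The conflict in the text is certain. The size rests on assumed event rates, an assumed 80% power and an assumed difference between omitted and observed patients. The true direction and size cannot be derived from the documents. It should be fixed because the missingness is avoidable and cheap to reduce.

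**What to change.** Amend the study-course text under Study Participants so that, unless consent is withdrawn, a patient with a pre-operative emergency remains in the study for data collection. Specifically:

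- Where the tumor is later resected, obtain Ki67 and caspase-3 with the sampling and scoring in Methods ("Six biopsies will be taken at time of colonoscopy and from the removed specimen") where feasible. Record the time from randomisation and the exposure to study drug. Where that sampling is not feasible, count the outcome as missing and do not substitute a routine block.
- Collect adverse events and, for those operated on, 30-day complications. The 30-day follow-up already provides that patients' "journals will be assessed for complications as well".
- Analyse every randomised patient with an outcome in the assigned arm, and report missing surgical tissue by arm and reason.
- Add two sensitivity analyses. The first fills missing surgical Ki67 with baseline Ki67 plus a range of shifts that includes the mean change in the placebo arm, because an unchanged baseline would assume no difference between biopsy and resection. The second omits tissue obtained after emergency surgery.
- Refer from the exclusion rule to the safety follow-up in Intervention and in Data and Adverse Events, so that the three passages agree.

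Nothing here concerns whether study drug is continued.

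The cost is protocol wording, specimens from perhaps 0 to 3 patients (more if emergencies are commoner than assumed) and a few journal reviews. Taking six biopsies around emergency surgery will not always be practical, which is why the sampling applies only where feasible. The first sensitivity analysis needs no new sampling, since inclusion already requires baseline material: "Sufficient amount of representative tumor material from the biopsies taken at the initial colonoscopy must be present". The drawback is that a few specimens will reflect short or interrupted exposure. The recorded exposure, the second sensitivity analysis and the planned per-protocol analysis will help show how much that matters.

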Immunohistochemical staining and analysis of Ki67 and cleaved caspase-3 tumor cell expression will be performed blinded and in collaboration with experienced pathologists. The immunohistochemical analyses

are performed on formalin-fixed paraffin-embedded tumor tissue. The level of proliferation will be defined as the percentage of tumor nuclei showing Ki67 staining in a specific microscopic field counted at the invasive front, and the level of apoptosis is defined as the absolute number of tumor cells expressing cytoplasmic and perinuclear staining of cleaved caspase-3 at the transition zone³⁹.

Height, weight and BMI are measured at time of preoperative examination and at time of surgery.

Blood samples from the patient before starting the medication, before surgery and at postoperative day 1, 2 and 10 are taken. Plasma from the patients are added to cultures with cancer cell lines in order to examine the effect on proliferation, migration and adhesion. This will be done in collaboration with researchers at Roskilde University at the department of science and environment, section of eukaryotic cell biology .

Blood samples will be analysed for Hgb, leucocytes and differential counts, CRP, thrombocytes, albumin, creatinine, eGFR, transaminases, glucose, Hba1c, insulin, c-peptide. These are needed to have baseline information about the patients and to be able to adjust for these variables in the multivariate analyses. If the HbA1c is 48mmol/mol or above the patient will be considered to be diabetic and may not be included. In this case the patient will be referred to his or her general practitioner.

Insulin resistance before and after surgery will be measured using the homeostatic assessment model (HOMA) from fasting levels of glucose and insulin. Capillary glucose level will be measured 4 times a day postoperatively on postoperative day 1 and 2 – before the main meals and before sleeping.

Composition of the microbiome in fecal and blood samples will be analysed using 16S rRNA sequencing.

A biobank will be created to store the tumor samples, gut samples, fecal samples, liver biopsies and additional blood samples for later analyses. The purpose of this is to ensure uniform analyses. The bio-bank will be created as soon as the approval from the Danish Data Protection Agency has been achieved, and all requirements concerning creation and maintenance of a bio-bank will be kept.

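### The primary Ki67 measure is defined at the invasive front, but the plan designates no baseline tissue from there; on the natural reading, Ki67 tissue at both times is random tumour-surface biopsies

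*Combined protocol and SAP*

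**What the plan says.** EFFECT PARAMETERS makes the primary outcome the level of proliferation at surgery, adjusted for the level at colonoscopy. It defines that level as a percentage of Ki67-stained tumour nuclei in a particular field and gives no tumour location. METHODS repeats the definition and adds one: "percentage of tumor nuclei showing Ki67 staining in a specific microscopic field counted at the invasive front".

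On tissue, STUDY PARTICIPANTS says: "The biopsies taken at the colonoscopy and biopsies from the specimen removed at surgery will be analyzed for Ki67". METHODS says of the analysis: "The same analysis will be repeated at the time of surgery on samples from the removed tumor". It then describes the sampling: "Six biopsies will be taken at time of colonoscopy and from the removed specimen", followed by "The biopsies are taken randomly from the tumor surface". It also plans a within-patient comparison: "The expression of cell proliferation and apoptosis will be compared to results from the preoperative biopsy analysis".

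The invasive margin appears as a sampling site once, under the immunoscore: "From the tumor at time of operation biopsies from the core and from the invasive margin will be taken". The use named for that tissue is: "These biopsies are stained for CD3 and CD8 positive lymphocytes". The inclusion criteria ask for enough representative tumour material in the colonoscopy biopsies and do not mention the front. STORAGE OF BIOLOGICAL MATERIAL gives an approximate size for the tumour samples, without depth or site.

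**The concern.** A baseline-adjusted outcome needs the same quantity measured twice. The only location stated for the primary measure is the front. The tissue assigned to that measure is described, on its natural reading, as random surface tissue. The plan treats margin tissue as something separate, taken only at surgery and for another stain.

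If the rule were applied as written, two things could follow. Patients whose colonoscopy biopsies contain no front would have no baseline value, and the plan gives no rule for that case. Alternatively, baseline would be read at the surface and surgery at the front. The baseline might then predict the surgical value less well, so the adjustment would gain less. The before-after comparison in METHODS would reflect a change of site as well as any effect of treatment.

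**Working it through.** **Comparing the texts**

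| Item | Colonoscopy | Surgery |
|---|---|---|
| Tissue assigned to Ki67 | Biopsies | Biopsies from the specimen, also described as samples from the removed tumour |
| Sampling described in METHODS | Six, random, tumour surface | Six, random, tumour surface (natural reading) |
| Margin tissue planned | None | Yes; only CD3 and CD8 named |
| Location in the Ki67 definition | Invasive front | Invasive front |

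The last row agrees with the second in neither column, and at colonoscopy no planned tissue would satisfy it by design. At surgery, margin tissue exists, but no section assigns Ki67 to it.

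**What the plan's figures allow**

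The sample size section gives 24 per arm but no target difference, SD or power. Its figure therefore cannot be reproduced. No correlation between baseline and surgical Ki67 is given, nor any rate of missing front tissue, so the loss cannot be derived.

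**Illustration only**

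Inputs from the documents: 24 per arm; two-sided 5%. Assumed: 80% power; correlation r of 0.3, 0.5 or 0.7; 4 missing baselines per arm.

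1. No usable baseline, two-sample t-test, noncentral t with 46 degrees of freedom: the detectable difference is 0.826 SD.
2. Usable baseline: 0.826 × √(1 − r²).

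| Assumed r | Detectable difference (SD) | Largest loss if the baseline becomes uninformative (SD) |
|---|---|---|
| 0.3 | 0.788 | 0.826 − 0.788 = 0.038 |
| 0.5 | 0.715 | 0.826 − 0.715 = 0.111 |
| 0.7 | 0.590 | 0.826 − 0.590 = 0.236 |

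These losses assume that every patient stays in the model.

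3. Four of 24 baselines missing per arm, r = 0.5, patients kept with a missing-baseline indicator. The average residual variance is (20 × 0.75 + 4 × 1)/24 = 0.792, giving 0.826 × √0.792 = 0.735 SD. In a simulation of 20,000 trials, power was 79.1% at 0.735 SD and 80.0% at 0.745 SD, so about 0.74 SD is fair.
4. Same case with those patients dropped, 20 per arm: the t-test value is 0.909 SD, and 0.909 × √0.75 = 0.787, about 0.79 SD.

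For r = 0.5, the assumed missing-data case therefore costs about 0.02 SD (0.735 − 0.715) if patients are kept and about 0.07 SD (0.787 − 0.715) if they are dropped.

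**The case against.** The strongest reply is that surface tissue at both times is plainly what is meant, that reading is blinded, and that nothing is then lost. Most of this stands. It is the most natural reading, and under it the only fault is that the stated definition is not the one applied. But the location is written into the definition of the primary measure, and no section withdraws it.

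Several further points are fair:

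- STUDY PARTICIPANTS does not mention the surface, and the wording in METHODS about the removed tumour is not restricted to it. The surface reading at surgery depends on taking the sampling sentence to cover both times. If surgery is instead read at the front, the two times differ in site.
- The documents define neither tumour surface nor invasive front. A reader might infer that a surface biopsy can never contain front, so that baseline Ki67 cannot be measured at all. The documents do not support that. Some biopsies may contain front; the plan simply neither requires nor checks it.
- A reader might see a contradiction between EFFECT PARAMETERS and METHODS. A shorter definition in the outcome section is not a contradiction. The conflict is between the definition and the sampling plan, both in METHODS.
- Both sections close the sentence that defines Ki67 and caspase-3 with a citation. Whether that source gives a field-selection rule cannot be checked here, so the absence of a general field rule is at most missing detail in this text.
- Reading surgery at the front would also need Ki67 staining of margin tissue, which no section plans.

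**Conclusion.** The point holds as a conflict between the stated definition of the primary measure and the tissue planned for it. It should be fixed, and confidence in the mismatch itself is high.

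Its consequences are limited. A reader might infer that the treatment comparison is biased. It is not: allocation is randomised, reading is blinded, and the same rule applies in both arms. What is exposed is the value of the baseline adjustment, the completeness of baseline data, and the meaning of the within-patient change.

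The loss is zero if surface tissue is read at both times; otherwise its size is unknown. A reader might take the 0.24 SD above as the expected loss. It requires an assumed correlation of 0.7 to fall to zero for every patient, and nothing in the documents indicates that. Nor is it a full upper bound, because dropping patients without a baseline would add to it. No conclusion here rests on the SD figures.

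**What to change.** Before the first reading, amend the definition in METHODS so that Ki67 is counted in the same type of tissue at both times, namely the random tumour-surface biopsies already planned, and delete the reference to the invasive front.

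The cost is a text amendment. No new biopsy or stain is needed, because Ki67 is already planned on this tissue at colonoscopy and at surgery. The downside is that the primary measure no longer describes the invasive front.

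Keeping the front as the primary site has no evident route: patients are included after the diagnostic colonoscopy, and no baseline tissue from the front is identified. A front reading at surgery could be kept as a secondary description, but only if the margin tissue already being taken can be used for it.

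For cleaved caspase-3, check whether the transition zone named in its definition can be identified in these biopsies. If it cannot, use the same matched tissue.
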